### **Revision history**

Version	Date
1.0	2023-09-24
1.1	2023-12-11
1.2	2024-01-16

## 1 Introduction

### 1.1 Background and rationale

Many girls lack basic knowledge, facilities and/or materials for managing menstruation safely and with dignity. Improving menstrual health (MH) can lead to sustained long-term benefits to education, health, and development [1,2]. Many governmental and non-governmental organisations are interested in introducing interventions to improve MH. However, there is a lack of evidence to guide policies and ensure interventions are effective [3,4].

Our formative studies in Uganda contributed to evidence that poor menstrual health is a key factor associated with anxiety among girls and with missing secondary school or class [5]. An effective intervention needs to address lack of knowledge of puberty and menstruation and the social environment (to reduce stigma), as well as practical methods to enable girls to better manage their periods (i.e. pad provision, education about effective pain management, and improvements to school toilet facilities). Our pilot study conducted in Wakiso District in 2017-2018 suggested that an intervention addressing these elements can potentially improve education and mental health outcomes, but a randomised controlled trial is needed for definitive results to drive forward policy changes [6,7].

The MENISCUS intervention consisted of five elements: i) training teachers to improve puberty education, ii) a student-led drama skit about MH, iii) training school members to deliver MH education sessions alongside the distribution of a menstrual kit containing reusable menstrual products, iv) provision of analgesics, and v) improvements to school WASH facilities. In each school, a "Menstrual Health Action Group" consisting of teachers, students, and parents is set up to help coordinate the intervention package.

### 1.2 Primary objective

To evaluate whether the MENISCUS intervention improves i) educational attainment based on the Mathematics, English, and Biology curriculum taught during the intervention delivery, and ii) reduces mental health symptoms among secondary school girls in Uganda.

#### 1.3 Secondary objectives

- 1) To evaluate whether the MENISCUS intervention improves the following secondary outcomes:
  - Knowledge of puberty and menstruation; attitudes towards menstruation (female and male participants, stratified by gender)
  - Menstrual practices at the last menstrual period (LMP)
  - Practice of pain management during LMP
  - Self-efficacy in addressing menstrual needs at LMP
  - Quality of life
  - Prevalence of symptomatic urinary tract infections (UTIs)
  - School and class absence during menses (in a random subsample of female participants)
  - School and class absence overall (in a random subsample of female participants)
  - Self-confidence in mathematics and in science abilities

- 2) To conduct a process evaluation to assess whether the intervention was implemented with fidelity, and to understand the contextual factors affecting the implementation, the acceptability to participants and the intervention mechanisms
- 3) To evaluate the costs of setting up and running the intervention package, the unit cost per female student reached and the incremental cost-effectiveness of the intervention per unit increase in selected policy-relevant outcomes, relative to optimised usual care
- 4) To assess the policy environment around menstrual health in Uganda, focusing on how implementing the intervention contributes to, and aligns with, the attainment of the Government policy objectives on MH management in schools

This Statistical Analysis Plan covers the analysis of the primary and secondary outcomes (Primary Objective and Secondary Objective 1).

### 1.4 Hypotheses

We hypothesised that improved educational attainment, mental health outcomes, and related healthand well-being outcomes will be achieved by improving self-efficacy for MH in Ugandan secondary schools, through improving the MH social and physical environment, and supporting girl's behavioural capability and observational learning.

## 2 Study Design

### 2.1 Trial design

The study was a parallel-arm, cluster-randomised controlled trial with a mixed-methods process evaluation, and economic and policy analyses. Schools (clusters) were randomised 1:1 to immediate delivery of the MENISCUS intervention or optimised usual care (provision of government menstrual management readers and circular). Schools randomised to the optimised usual care arm were offered the intervention after the endline assessment (approximately 1 year after randomisation). In this SAP, the term "intervention" refers to immediate intervention, and "control" to optimised usual care (delayed intervention, delivered after endline).

Female students who joined the S2-S3 class cohort during the intervention delivery period were eligible to be recruited. This "open cohort" design accommodates the dynamic school population, as students may both join and leave the class cohort during the intervention period. In the pilot study, 82% of participants present at baseline were present at the endline survey 9 months later [6]. Primary and secondary outcomes for female students will be assessed among participants present at endline, adjusting for cluster-level mean baseline measures of the relevant outcome where available. Knowledge and attitudes among male students will be assessed through a closed cohort. Further details are described in section 3.4 below.

### 2.2 Changes to the design and analyses

A detailed description of all protocol amendments is included on pages 2-3 of the trial protocol version 6.0. Additional modifications to the measures defined for each secondary outcome are described in section 4.3 and Annex 2.

The secondary outcome on prevalence of bacterial vaginosis (BV), vaginal yeast and urinary tract infections (UTIs) among symptomatic girls was revised to the prevalence of UTIs only among symptomatic girls. This change was approved by the TSC to remove the time burden on schools, participants, and data collection teams.

The study protocol version 5.0 states that data will be analysed using mixed models for repeated measures (MMRM). This has been revised to mixed models adjusting for cluster level mean at baseline as described in section 0, as data were collected at only two time points.

### 2.3 Sample size

The sample size of 60 schools was based on an anticipated harmonic mean of 60 female participants per school at endline. This sample size provides 84% power to detect a standardised mean difference of 0.2 for continuous outcomes, assuming an intra-cluster correlation ( $\rho$ ) of 0.05 and type 1 error of 0.05. The effect size of 0.2 is that observed for the primary outcome of SDQ score for girls in the pilot [6] and is considered moderate for educational outcomes and hence of policy relevance. The harmonic mean was used to account for variation in school size. We have not adjusted the type 1 error because the two primary outcomes are independent, and an improvement in one without the other will be informative.

The subsample of 1500 girls selected to provide daily diary data on school/class attendance and their menstrual cycle over 40 school days at endline provides >98% power to detect a 20% relative reduction on period-days at endline, based on pilot data [6] and ~89% power to detect this difference by district or other equally sized subgroups. From our pilot, we expect >95% of girls to be menstruating at endline, and this is accounted for in the power calculations where relevant.

Revised power calculations were conducted in March 2022 and reported to the IDMEC in April 2022 (report 1), following indication that due to COVID-19 closures and other reasons the harmonic mean school size may be smaller than 60. This showed that a harmonic mean of 40 female students per school at endline provides 80% power to detect a standardised mean difference of 0.2 assuming an ICC of 0.05.

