### 2.4 Randomisation

The 60 trial schools were allocated using 1:1 restricted randomisation. Within each district, the schools were additionally stratified by median UNEB baseline examination score (high/low). Covariate-constrained randomisation was then used to minimise imbalance with respect to key school-level factors (mean baseline examination score, mean past school examination scores, mean baseline SDQ score, government vs. private school, mean score on the Menstrual Practice Needs Scale, menstrual cup uptake, and the number of S2 female participants). Stratification factors (district and high/low baseline examination score) will be included as fixed-effects in all analyses.

A list of 1000 eligible allocations was randomly generated from all allocations meeting the specified balance criteria. One allocation was randomly selected at semi-public randomisation ceremonies held in each district in the presence of representatives from schools, the District Education Officer (DEO), and the Ministry of Education and Sports (MoES), and Ministry of Health (MoH).

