#### 6.2 Multiple testing adjustment

The two primary outcomes are considered independent due to different causal mechanisms, so an improvement in one without the other will be informative. According to FDA and EMA guidelines, we shall adjust the Type 1 error for multiple testing using the Benjamin-Hochberg (BH) procedure [14]. The procedure states that for the two primary outcomes considering a false discovery rate (FDR) of 0.05: 1) if the larger p-value  $\leq 0.05$ , then there is evidence for both end points; 2) if the larger p-value >0.05, then the smaller p-value should be  $\leq 0.025$  to show evidence for that endpoint, and 3) if the larger p-value >0.05, then there is no evidence for both endpoints. Despite this procedure, interpretation of the intervention effect will focus on effect sizes and confidence intervals rather than p-values.

For the secondary outcomes, specific inferences will be made for each individual null hypothesis and multiple testing adjustment will not be performed. Given the number of tests performed, the intervention effects will be interpreted with caution [15,16].

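### Section 2.3 leaves the type 1 error unadjusted and Section 6.2 adjusts it by Benjamini-Hochberg; the stated 84% and 80% power are unadjusted figures, and the two sections need reconciling

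*SAP*

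**What the plan says.** SAP Section 2.3 sizes the trial as follows: "The sample size of 60 schools was based on an anticipated harmonic mean of 60 female participants per school at endline". It continues: "This sample size provides 84% power to detect a standardised mean difference of 0.2 for continuous outcomes", at an ICC "of 0.05 and type 1 error of 0.05". On multiplicity it says "We have not adjusted the type 1 error because the two primary outcomes are independent", adding that a gain in one outcome alone would still be informative. The March 2022 recalculation, for a harmonic mean of 40, "provides 80% power to detect a standardised mean difference of 0.2 assuming an ICC of 0.05"; the type 1 error is not restated there.

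SAP Section 6.2 opens with the same two reasons, independence and the value of a result on one outcome alone, and then says "we shall adjust the Type 1 error for multiple testing using the Benjamin-Hochberg (BH) procedure". At a false discovery rate of 0.05 it lists three items:

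1. Larger p-value at or below 0.05: evidence for both outcomes.
2. Larger p-value above 0.05: the smaller must be at or below 0.025 to show evidence for its outcome.
3. Larger p-value above 0.05: no evidence for either.

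Section 2.2, which covers changes to design and analyses, does not mention multiplicity.

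**The concern.** The same rationale leads to opposite statements about the same two outcomes. The difference can decide a primary result. With p-values of 0.03 and 0.40, an unadjusted 0.05 counts the first outcome as positive, while item 2 of Section 6.2 does not. If both null hypotheses are true and the tests are independent, the chance of at least one false positive is 1 − 0.95² = 9.75% unadjusted. Under the Benjamini-Hochberg rule it is 1 − 0.975² + 0.025² = 5%.

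The stated power is also tied to the unadjusted threshold. The gap is largest when only one outcome responds, which is the case both sections single out as informative.

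**Working it through.** **Inputs.** There are 60 schools (Section 2.3), and "The 60 trial schools were allocated using 1:1 restricted randomisation" (Section 2.4), so k = 30 per arm. The standardised mean difference is 0.2, the ICC is 0.05, and the harmonic mean cluster size m is 60 or 40 (Section 2.3). Sidedness is not stated; two-sided is taken because it reproduces the figures.

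**Standard error.** Design effect DE = 1 + (m − 1) × 0.05; SE = √(2 × DE / (k × m)); noncentrality = 0.2 / SE.

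- m = 60: DE = 3.95; SE = √(7.90/1800) = 0.0662; noncentrality 3.02.
- m = 40: DE = 2.95; SE = √(5.90/1200) = 0.0701; noncentrality 2.85.

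**Reproducing the plan.** Noncentral t with 58 degrees of freedom, critical values 2.002 (two-sided 0.05) and 2.301 (two-sided 0.025):

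| m | Stated | Power at 0.05 | Power at 0.025 |
|---|---|---|---|
| 60 | 84% | 84.3% | 76.2% |
| 40 | 80% | 80.1% | 70.8% |

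A normal approximation gives 85.5% and 81.4% at 0.05, and 78.2% and 72.9% at 0.025. Using k − 1 schools per arm gives 84.3% and 80.1%, then 76.6% and 71.3%. On every variant, 0.05 matches the plan to within 2 points and 0.025 does not.

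**Power under Section 6.2 (items 1 and 2).** An outcome succeeds if its p-value is at or below 0.025, or if it lies between 0.025 and 0.05 and the other outcome's p-value is at or below 0.05. With independent outcomes:

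power = P(0.025) + [P(0.05) − P(0.025)] × q,

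where q is the chance that the other outcome reaches 0.05. So q = 0.05 if the other has no effect, and q equals its own power if it has the planned effect.

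- m = 60, other null: 0.762 + 0.082 × 0.05 = 76.6%.
- m = 60, both 0.2: 0.762 + 0.082 × 0.843 = 83.1%.
- m = 40, other null: 0.708 + 0.092 × 0.05 = 71.3%.
- m = 40, both 0.2: 0.708 + 0.092 × 0.801 = 78.2%.

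**Correlation (assumed range 0 to 0.5, by simulation).** With both outcomes effective, power at correlation 0.5 is 82.3% and 77.5%. With the other outcome null it barely moves (76.6% and 71.1%).

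**Item 3 as printed.** Items 2 and 3 share a condition and reach different conclusions. Taken literally, item 3 lets neither outcome succeed unless both p-values are at or below 0.05. With both effects at 0.2 and independence, that has probability 0.843² = 71% (m = 60) or 0.801² = 64% (m = 40).

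**The case against.** **The power figures are not miscalculated.** This stands. They are right at their stated inputs, and Section 2.3 says openly that no adjustment was made.

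**Section 2.3 records how the trial was sized, and Section 6.2 governs the analysis.** This is a fair reading: the first sits under the sample size heading in the past tense, and the second is prospective and gives thresholds. So it would go too far to say that a reader cannot tell which threshold applies. But Section 2.3 does not limit itself in this way, Section 2.2 records no change, and no power is given for the rule that will be used.

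**The final model may recover the loss.** Section 5.2 adjusts for the school-level baseline mean and the stratification variables. If these explained 10%, 25% or 50% of between-school variance (assumed values; t with 55 degrees of freedom), power under Section 6.2 with the other outcome null would be about 80%, 85% or 94% at m = 60, and about 74%, 80% or 88% at m = 40. The SAP gives no such proportion, and the gain would raise unadjusted power too. The like-for-like loss at the plan's own inputs remains, but the recalculated figures must carry their assumptions and are not a forecast of delivered power.

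**The practical effect is limited.** Outcomes were assessed in June to August 2023, before SAP version 1.0 (September 2023), and Section 6.2 puts effect sizes and intervals ahead of p-values. Restating power alters no estimate or interval.

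**A stronger inference to avoid.** A reader might conclude that the power reported to the oversight committee in April 2022 was overstated. The SAP does not support this. That report is not shown, and nothing indicates that Benjamini-Hochberg was planned then.

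**Conclusion.** The inconsistency between Sections 2.3 and 6.2 is real and should be resolved. The stated 84% and 80% are powers of a single unadjusted two-sided test at 0.05. For the 80% figure this is inferred from its reproducing at that level.

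Under items 1 and 2 of Section 6.2, the loss depends on the other outcome. It is about 8 points (m = 60) or 9 points (m = 40) if that outcome has no effect. If both have the planned effect and are independent, it is only about 1 to 2 points, rising to roughly 2 to 3 points at an assumed correlation of 0.5. All figures assume 30 schools per arm, ICC 0.05, a difference of 0.2 and no gain from baseline adjustment.

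Pointing to Section 6.2 does not settle the rule while its item 3 contradicts item 2.

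**What to change.** 1. In Section 2.3, keep the sentence on not adjusting as a record of sizing, but qualify it: the original and revised power were calculated at unadjusted two-sided 0.05, and Section 6.2 governs the analysis.
2. Add per-outcome power under Section 6.2: about 77% (m = 60) and 71% (m = 40) if the other primary outcome has no effect, and about 83% and 78% if both have a difference of 0.2. State the assumptions beside them: independent outcomes, ICC 0.05 and no gain from baseline adjustment.
3. In Section 6.2, change the condition of item 3 so that no evidence is claimed for either outcome when the smaller p-value is above 0.025 and the larger is above 0.05.

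The cost is a few lines of SAP text and a somewhat less favourable power statement. Sample size, data collection and models are unchanged.

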### 2.4 Randomisation

The 60 trial schools were allocated using 1:1 restricted randomisation. Within each district, the schools were additionally stratified by median UNEB baseline examination score (high/low). Covariate-constrained randomisation was then used to minimise imbalance with respect to key school-level factors (mean baseline examination score, mean past school examination scores, mean baseline SDQ score, government vs. private school, mean score on the Menstrual Practice Needs Scale, menstrual cup uptake, and the number of S2 female participants). Stratification factors (district and high/low baseline examination score) will be included as fixed-effects in all analyses.

A list of 1000 eligible allocations was randomly generated from all allocations meeting the specified balance criteria. One allocation was randomly selected at semi-public randomisation ceremonies held in each district in the presence of representatives from schools, the District Education Officer (DEO), and the Ministry of Education and Sports (MoES), and Ministry of Health (MoH).

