### 5.2 Analysis of continuous outcomes

The intervention effect for each primary outcome (educational attainment and SDQ) and continuous secondary outcomes will be presented as the adjusted mean difference in the endline scores between arms with corresponding 95% confidence intervals (CI). The effects will be estimated using linear random-effects (RE) models using a random intercept for school to adjust for within-school clustering. The model will be adjusted for the cluster-level mean of the baseline outcome measure and stratification variables (district and high/low school-level UNEB score). Likelihood ratio tests (LRT) will be used to obtain p-values. The results will be presented as shown in Table A5.

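### Five of the seven factors that constrained the randomisation are in neither primary model; if they are prognostic, the confidence intervals will be wider than they need to be

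*SAP*

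**What the plan says.** SAP section 2.4 describes two layers of restriction. Schools were stratified by district and by high or low baseline exam score. Then "Covariate-constrained randomisation was then used to minimise imbalance with respect to key school-level factors". Seven factors are listed: mean baseline exam score, mean past exam scores, mean baseline SDQ, government or private ownership, mean MPNS score, menstrual cup uptake, and number of S2 girls. One allocation was drawn from a list of 1000 that met balance criteria which the SAP does not state.

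Only the first layer reaches the models: "Stratification factors (district and high/low baseline examination score) will be included as fixed-effects in all analyses". For continuous outcomes, section 5.2 adds one term: "The model will be adjusted for the cluster-level mean of the baseline outcome measure and stratification variables". The footnotes to Tables A5, A6 and A7 give the same covariates. P-values come from likelihood ratio tests (LRT).

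Section 5.7 plans no analysis with the remaining constraint factors and no randomisation-based test. Ownership and S2 size return only as effect modifiers in Table 3. No reason for the omission is given.

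**The concern.** Constraining the allocation removes chance imbalance in the constrained factors, so the true variance of the estimated effect falls if those factors predict the outcome. A model that omits them still counts the between-school variance they explain as error. Its standard error then overstates the true one, and part of what the constrained design bought does not appear in the interval.

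Each primary model lacks six of the seven factors in the form in which they were constrained. Five are in neither model. The attainment model also lacks SDQ, and the SDQ model has the exam score only as high/low. Interval width matters here because section 6.2 says interpretation will rest on effect sizes and confidence intervals rather than p-values.

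**Working it through.** **The plan's own figures.** The inputs are in section 2.3: "The sample size of 60 schools was based on an anticipated harmonic mean of 60 female participants per school at endline", a standardised difference of 0.2, an intra-cluster correlation of 0.05 and type I error of 0.05 (taken as two-sided). With 30 schools per arm and m girls per school, the design effect is 1 + (m − 1) × 0.05 and the effective n per arm is 30m divided by it.

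- m = 60: design effect 3.95; effective n 1800/3.95 = 455.7; standard error √(2/455.7) = 0.0662; power 85.5% (normal) or 84.3% (t, 58 df). Stated: 84%.
- m = 40: design effect 2.95; effective n 1200/2.95 = 406.8; standard error 0.0701; power 81.4% (normal) or 80.1% (t, 58 df). Stated: 80%.

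Both reproduce, and neither assumes any gain from covariates or from the constraint.

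**What the omission costs.** The SAP gives neither the prognostic strength of the factors nor the tightness of the balance criteria, so this was simulated over a range. Set-up: school-level means, 60 schools in four strata, equal school sizes, uncorrelated factors, 3000 runs per scenario. Assumptions: the eligible set is the best 10% of 400 candidate allocations, balanced on the own baseline mean and six other factors; the own baseline mean explains 30% of between-school variance; the six others explain a further 0%, 10% or 30%. Inference is t-based. Each pair is the SAP model → the model with all constrained factors.

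| m | Extra variance | 95% CI width | Ratio | Power at 0.2 | Type I error, SAP model |
|---|---|---|---|---|---|
| 60 | 0% | 0.233 → 0.238 | 0.98 | 91.5 → 90.6% | 5.4% |
| 60 | 10% | 0.234 → 0.226 | 1.04 | 92.7 → 93.7% | 4.4% |
| 60 | 30% | 0.233 → 0.199 | 1.17 | 94.4 → 97.7% | 3.1% |
| 40 | 0% | 0.249 → 0.254 | 0.98 | 88.5 → 87.4% | 5.0% |
| 40 | 10% | 0.251 → 0.244 | 1.03 | 89.0 → 89.9% | 3.8% |
| 40 | 30% | 0.251 → 0.221 | 1.14 | 90.5 → 94.5% | 2.8% |

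Monte Carlo error is about 0.4 points for type I error and up to 0.6 for power.

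The mechanism shows when the SAP model's average standard error is set against the actual spread of its estimates. At m = 60 these are 0.0582 and 0.0588 (0% extra), 0.0583 and 0.0559 (10%), and 0.0583 and 0.0514 (30%, a ratio of 1.13). The estimate becomes more precise, but the reported standard error does not move.

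If the own baseline mean explains 50% instead, the width ratios at m = 60 and 40 are 0.209/0.200 = 1.05 and 0.228/0.220 = 1.04 for 10% extra, and 0.209/0.169 = 1.24 and 0.228/0.194 = 1.18 for 30%.

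**The planned test.** Section 5.2 specifies an LRT, not a t test. On school means with 60 schools, the maximum-likelihood LRT rejects when 60 × ln(1 + t²/df) > 3.84, that is when t² > df × (e^(3.84/60) − 1) = 0.0661 × df.

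- SAP covariates (intercept, arm, two strata terms, baseline mean): 60 − 5 = 55 df, cut-off |t| = 1.91, true level 6.2%.
- Four factors added: 51 df, 1.84, 7.2%.
- Six factors added: 49 df, 1.80, 7.8%.

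In the simulation, the LRT for the SAP model had type I error of 6.7%, 5.3% and 3.8% (m = 60) and 6.2%, 4.9% and 3.7% (m = 40) at 0%, 10% and 30% extra variance. With all six factors added it was 7.0–8.1%.

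**The case against.** The strongest reply is that the loss is conditional. The factor closest to each primary outcome is already in its model as the baseline mean, and the high/low exam stratum is in both. Past exam scores may largely repeat the baseline exam score. If the rest adds nothing, the SAP model is the slightly better one, by about 1 point of power. This stands, and it is why the size is given as a range. It does not justify leaving out, without a stated reason, factors that the SAP itself treats as key in the randomisation.

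Two stronger readings are tempting, and the SAP supports neither. A reader might infer that the trial falls short of its stated power. It does not: 84% and 80% reproduce with no adjustment, and under the table's assumptions the SAP model has about 88–94%. A reader might also infer that both primary tests run below 5%. The t-based results fall below 5% when the factors are prognostic, but the planned test is an uncorrected LRT, whose small-sample excess works the other way. Its simulated level falls clearly below 5% only at 30% extra variance.

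The objection that merely adding covariates would do harm is right as far as it goes. Under the uncorrected LRT the level would rise to about 7–8%, so adjustment has to come with a small-sample correction.

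**Conclusion.** The point holds as forgone precision. The randomisation used seven factors, and the analysis keeps the strata and the outcome's own baseline mean. If the omitted factors explain a further 10% of between-school variance, intervals are about 3% wider and about 1 point of power is forgone. At 30%, intervals are about 14–17% wider and 3–4 points are forgone. At 0%, nothing is lost and adjustment costs about 1 point.

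These figures rest on an assumed best-10% constraint, on the own baseline mean explaining 30% of between-school variance, on equal school sizes and uncorrelated factors, and on t inference. The omission is not shown to bias the estimated effect. This is a cheap improvement, not a flaw that undermines the trial.

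**What to change.** In sections 2.4 and 5.2 and the Table A5 footnote, add a short pre-specified set of constraint factors as school-level fixed effects in the two primary models: at least ownership, mean past exam score, continuous mean baseline exam score and number of S2 girls. The continuous baseline exam score is already the baseline term for attainment, so this adds four terms for SDQ and three for attainment. Keep the present model as a sensitivity analysis.

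For these models, replace the uncorrected LRT with small-sample inference: REML with Kenward-Roger or Satterthwaite t or F tests, or a t test on between-school degrees of freedom. A permutation test over the eligible allocations can supplement this; it gives a p-value that respects the restriction but does not by itself correct the model-based intervals.

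The cost is SAP wording and about four to six of some 55 school-level degrees of freedom. No new data are needed, because these factors were used to randomise all 60 schools. The change should be made before unmasking. If the sponsor prefers the present model, the SAP should say why the constraint factors are left out.
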